o First dose of the study intervention will be administered IV. A second dose is to be administered SC 4 to 6 hours after the IV dose on Day 1 followed by daily SC dose administration. A time window of \pm 1 hour is allowed for the daily SC study intervention administrations. Exception to this regimen: If a participant has received and tolerated a single dose of marketed caplacizumab intravenously (IV) for the presenting episode of iTTP within 4 hours prior to enrollment, the IV dose of study intervention at 0H will be skipped and the subcutaneous dose of caplacizumab due at 4-6H relative to the pre-study dose will be the first dose of study intervention. All subsequent doses will continue to follow the schedule as outlined in [Section 1.3.4](#) below. Please see [Section 1.3.4](#) below for details.

p For participants for whom TPE needs to be started only: TPE with plasma (eg, fresh frozen plasma, solvent detergent/viral-inactivated plasma, cryosupernatant) at 1 to 1.5 \times estimated plasma volume daily as of enrollment. See details in [Section 4.1](#).

q Recommend starting anti-CD20 antibody therapy (rituximab or biosimilar) once iTTP diagnosis is confirmed (ADAMTS13 level <10%) and is required if ADAMTS13 level remains <10%, 1 week after platelet count normalization or stop of TPE (if TPE was started).

s

1.3.3 Schedule of activities: Treatment and follow-up period (may include in-hospital & out-patient visits)

Study Period	Treatment Period (maximum 12 weeks)	Early Treatment Discontinuation Visit (\pm 3 days after last dose intake)	Follow-up Period ^l				
			FU Visit 7 days after last dosing (\pm 1 day)	Additional ^t FU Visit 14 days after last dosing (\pm 1 day)	Additional ^t FU Visit 21 days after last dosing (\pm 1 day)	FU visit 28 days after last dosing (\pm 1 day)	FU visit (EOS) 12 weeks after last dosing (\pm 3 days)
Study treatment administration							
IMP administration (daily) ^b	x						
Therapeutic plasma exchange (if needed) ^c	x						
Corticosteroids	x						
Anti-CD20 antibody therapy ^d	x						
eDiary (IMP administration info) ^e	x	x					
Safety and laboratory assessments							
Neurologic assessments ^f	x	x				x	x
GCS	x	x					x
Clinically significant TTP event	x	x	x	x	x	x	x
Bleeding assessment ^g	x	x	x	x	x	x	x
Physical examination	x	x	x	x	x	x	x
Vital signs ^h	x	x	x	x	x	x	x
12-lead ECG ⁱ	x	x				x	x
Adverse events	>						
Concomitant medication	>						
Clinical laboratory analyses ^j	x	x				x	x
Platelet count ^k	x	x	x	x	x	x	x

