There is limited availability of data on efficacy of caplacizumab without TPE as first-line therapy. There are published case reports for 11 acute episodes in 10 patients (2, 25, 26, 27, 28), treated with caplacizumab and immunosuppression without requiring TPE. All had platelet count recovery within 5 days. In the published case series by Volker et al, the platelet counts normalized ($>150 \times 10^9/L$) after median 84 hours (3.5 days) with a range of 48 hours to 96 hours (2- 4 days) (2). In the Phase 3 HERCULES study, the median time to normalization of the platelet count was shorter with caplacizumab than with placebo (2.69 days [95% CI, 1.89 to 2.83] vs. 2.88 days [95% CI, 2.68 to 3.56], $P = 0.01$). However, it is important to note that all HERCULES study patients had a TPE prior to study entry, and this may have shortened the time to platelet response. In the Phase 2 TITAN study, the median time to confirmed platelet response was 2.97 days (95% CI: 2.74, 3.65) in the caplacizumab group and 4.79 days (95% CI: 3.51, 5.94) in the placebo group. Majority of the patients in the TITAN study did not receive a prior TPE.

In summary, treatment with caplacizumab and immunosuppression without first-line TPE may reduce the morbidity and mortality associated with TPE-related complications. It will improve

[figure not shown]
patients' quality of life while reducing the overall iTTP related health care resource utilization and costs (ie, the number of days in intensive care unit (ICU), length of hospitalization and number of days and volume of plasma needed if requires TPE). Although, there is limited availability of data on efficacy of caplacizumab/Cablivi® without TPE as first-line therapy, there are published case reports for 11 acute episodes in 10 patients, treated with caplacizumab and IST without TPE. All patients showed platelet count recovery within 5 days and no new safety findings were reported.

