Study participants will not receive TPE as first-line therapy. However, participants may receive TPE if it is determined that there is lack of adequate response to treatment after first 24 hours or if there is any clinical deterioration at any time during the study, including during the first 24 hours (please see below for additional details). It is expected that the participant is hospitalized when the treatment is started, and the duration of initial hospitalization may vary based on clinical condition of the individual participant.

Caplacizumab treatment will be continued until sustained ADAMTS13 activity level of $\geq 50\%$ at 2 consecutive visits after platelet count normalization (defined as $\geq 150 \times 10^9/L \times 2$ consecutive values) or 12 weeks, whichever occurs first. Thus, the maximum treatment duration of caplacizumab will be 12 weeks for the presenting episode.

The post-treatment follow-up period will be 12 weeks. The anticipated study duration per participant without a recurrence while on therapy is maximum of approximately 24 weeks (ie, approximately 1 day for screening + maximum 12 weeks of treatment for the presenting episode + 12 weeks of follow-up).

Initial treatment regimen during hospitalization:

1. anti-vWF therapy: Caplacizumab

Recommended dose: Caplacizumab 10 mg (11 mg in US and Canada; see [Section 2](#)) intravenous (IV) for a single dose followed by caplacizumab 10 mg (11 mg in US and Canada) subcutaneous (SC) 4-6 hours after the IV dose (Day 1) (exceptions to this are detailed in [Section 1.3.4](#)). This will be followed by caplacizumab 10 mg (11 mg in US and Canada) SC daily starting on Day 2 for a maximum treatment duration of 12 weeks.

Note: The baseline ADAMTS13 activity level results from the local laboratory, available within 48 hours will be used to confirm the diagnosis of iTTP. It is expected that there will be minimal discrepancy between local and central laboratory ADAMTS13 activity levels. The central laboratory test results will be available only after 3-4 days.

- If the baseline central laboratory ADAMTS13 activity is <10% of normal → continue caplacizumab and IST.
- If the baseline central laboratory ADAMTS13 activity is between 10% - 20% of normal → use clinical judgment in deciding to continue or stop caplacizumab treatment after evaluation of the totality of signs and symptoms plus other laboratory data.

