- Immunosuppressive therapy will be continued as described earlier. If there is inadequate response to the initial immunosuppressive regimen (corticosteroids with or without anti-CD20 antibody therapy) and the ADAMTS13 activity level is <10% after 4 weeks of therapy, the Investigator may consider optimizing immunosuppression further (including adding anti-CD20 antibody if not done before) or consider alternative immunosuppressive therapies as per local standard of care.
- Laboratory monitoring of platelets and LDH will be performed weekly during the out-patient treatment phase and at the 3 follow-up visits*.
*Note: there will be two additional follow-up visits for participants who do not have ADAMTS13 activity levels of $\geq 50\%$ at the time of caplacizumab discontinuation.
- ADAMTS13 activity levels will be obtained once a week starting on Day 8 of caplacizumab treatment. If the ADAMTS13 activity level is <10% after 4 weeks of therapy, consider optimizing immunosuppression further.

If participant requires TPE:

- The participant will continue caplacizumab 10 mg (11 mg in US and Canada) SC daily until sustained ADAMTS13 normalization ($\geq 50\%$) at 2 consecutive visits after stop of daily TPE. During the time, the participant is receiving TPE, caplacizumab will be given after the TPE. The maximum treatment duration of caplacizumab is 12 weeks for the presenting episode.
- Immunosuppressive therapy will be continued as described earlier. If there is inadequate response to the initial immunosuppressive regimen (corticosteroids with or without anti-CD20 antibody therapy) and the ADAMTS13 activity level is <10% after 4 weeks of therapy, the Investigator may consider optimizing immunosuppression further (including adding anti-CD20 antibody if not done before) or consider alternative immunosuppressive therapies as per local standard of care.
- Laboratory monitoring of platelets and LDH will be performed weekly during the out-patient treatment phase and at the 3 follow-up visits*.
*Note: there will be two additional follow-up visits for participants who do not have ADAMTS13 activity levels of $\geq 50\%$ at the time of caplacizumab discontinuation.
- ADAMTS13 activity levels will be obtained once a week starting on Day 8 of caplacizumab treatment. If the ADAMTS13 activity level is <10% after 4 weeks of therapy, consider optimizing IST further.

Follow-up after treatment completion:

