Participants will be followed up for a period of 12 weeks after completion of study treatment. During the follow-up period they will be evaluated in the out-patient setting at 7 ± 1 days, 28 ± 1 days and 12 weeks (± 3 days) after the last dose of the IMP.

There will be two additional follow-up visits (14 ± 1 days and 21 ± 1 days after last caplacizumab dosing) for participants who do not have ADAMTS13 activity levels of $\geq 50\%$ at the time of caplacizumab discontinuation.

A physical exam will be performed, and laboratory tests including platelet count and organ damage markers will be obtained during the visits.

Treatment of a first clinical recurrence (exacerbation or relapse):

Clinical Exacerbation is defined as after a Clinical Response and before a Clinical Remission, platelet count decreases to $<150 \times 10^9/L$ (with other causes of thrombocytopenia excluded), with or without clinical evidence of new or progressive ischemic organ injury, within 30 days of stopping TPE or anti-vWF therapy.

Clinical Relapse is defined as after a Clinical Remission, platelet count decreases to $<150 \times 10^9/L$ (with other causes of thrombocytopenia ruled out), with or without clinical evidence of new ischemic organ injury. A Clinical Relapse must be confirmed by documentation of severe ADAMTS13 deficiency ($<10\%$).

In case of a first clinical recurrence (exacerbation or relapse) of the presenting TTP episode during the overall study period, it is up to the Investigators to adjust the ongoing treatment plan, which may include start or restart of TPE and adjustment of IST regimen and caplacizumab therapy. In case that caplacizumab treatment is maintained for a first clinical recurrence (exacerbation or relapse), the visit schedule will be the same as during the initial treatment period.

If a participant develops a second clinical recurrence (exacerbation or relapse) the participant will discontinue from the study ([Section 7.1.1](#)). At the time of discontinuing from the study, if possible, an early discontinuation visit should be conducted, as shown in the SoA ([Section 1.3](#)). See SoA for data to be collected at the time of study discontinuation and follow-up and for any further evaluations that need to be completed.

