9.2.2 Primary endpoint(s) analyses

The primary endpoint will be analyzed in mITT population.

The primary endpoint is the proportion of participants achieving remission without requiring TPE during the overall study period. Remission is defined as sustained Clinical Response with either (a) no TPE and no anti-VWF therapy for ≥ 30 days (Clinical Remission) or (b) with attainment of ADAMTS13 activity level $\geq 50\%$ (Complete ADAMTS13 Remission), whichever occurs first. Remission is assessed starting from the clinical response (for participants not requiring TPE) or the end of TPE (for participants requiring TPE), until the end of study.

Clinical response is defined as sustained platelet count $\geq 150 \times 10^9/L$ and LDH $< 1.5 \times$ ULN and no clinical evidence of new or progressive ischemic organ injury for at least 2 consecutive visits.

Clinical remission is defined as sustained Clinical Response with no TPE and no anti-vWF therapy for ≥ 30 days.

Complete ADAMTS13 Remission is defined as sustained Clinical Response with attainment of ADAMTS13 activity level $\geq 50\%$ for at least 2 consecutive visits during the overall study period.

Responders are participants who achieve remission without requiring TPE during the overall study period. Each participant will be classified as a responder or non-responder per the response criteria, and the proportion of responders will be calculated together with a 95% Wilson CI.

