3.2 PRIMARY ENDPOINT ANALYSIS

3.2.1 Definition of endpoint

The primary endpoint is the proportion of participants (responders) achieving **remission** without requiring TPE during the overall study period.

Remission is defined as sustained Clinical Response with either (a) no TPE and no anti-VWF therapy for ≥ 30 days (Clinical Remission) or (b) with attainment of ADAMTS13 activity level $\geq 50\%$ (Complete ADAMTS13 Remission), whichever occurs first.

Remission is assessed starting from the clinical response (for participants not requiring TPE) or the end of TPE (for participants requiring TPE), until the end of study.

Clinical response is defined as sustained platelet count $\geq 150 \times 10^9/L$ and LDH $< 1.5 \times$ ULN and no clinical evidence of new or progressive ischemic organ injury for at least 2 consecutive visits.

Clinical remission is defined as sustained Clinical Response with no TPE and no anti-vWF therapy for ≥ 30 days.

Complete ADAMTS13 Remission is defined as sustained Clinical Response with attainment of ADAMTS13 activity level $\geq 50\%$ for at least 2 consecutive visits during the overall study period.

Responders are participants who achieve remission without requiring TPE during the overall study period. Each participant will be classified as a responder or non-responder per the response criteria, and the proportion of responders will be calculated together with a 95% Wilson CI.

More details regarding the endpoint derivation are provided in [Section 5.4](#).

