- The values resulting from these derivations will be the values used for the graphical representation of platelet, LDH and ADAMTS13 activity from Day 4.

Consecutive laboratory assessments are considered as 'consecutive visits' for efficacy endpoints.

A participant could potentially have missing laboratory assessment data, however, remission could still be confirmed at a subsequent laboratory value. In the case there is inadequate information to determine the remission status of a participant by the end of the study, the participant will be treated as not having achieved remission.

Clinical evidence of new or progressive ischemic organ injury

Clinical evidence of new or progressive ischemic organ injury is defined as any presence of following clinically significant iTTP event:

- Neurological event
- Elevated cardiac troponins
- Acute myocardial infarction
- Conduction abnormality
- Repolarization abnormality
- Heart failure
- Clinically significant renal event

which will be identified from the checkboxes in the "Clinically Significant TTP Event" eCRF form.

Exacerbation of TTP, Relapse of TTP and Other event will not be considered as clinical evidence of new or progressive ischemic organ injury.

Sustained Clinical Response

Sustained Clinical response is defined by the concomitance of the 3 following criteria for at least 2 consecutive visits (starting from D2):

- platelet count $\geq 150 \times 10^9/L$
- LDH $< 1.5 \times ULN$
- no clinical evidence of new or progressive ischemic organ injury

Remission

Remission is defined as (1) a sustained Clinical response (see above) associated with (2) Clinical remission or (3) Complete ADAMTS13 Remission, whichever occurs first, and defined as:

- Clinical remission: No TPE (*Plasma Exchange* form) and no anti-VWF therapy (Caplacizumab treatment) for ≥ 30 days (from the date that Clinical Response is achieved).
- Complete ADAMTS13 Remission: The attainment of ADAMTS13 activity level $\geq 50\%$ for at least 2 consecutive visits (starting from D2).

Time to event

For each of below time to event, in case of no observation of the event or death, the censoring date will be defined as the last non-missing value of the analyzed parameter (platelet count, LDH....) if any, else as the start date of treatment (defined as first caplacizumab administration [whatever marketed or study IMP]).

- Time to platelet count response will be calculated as follow:

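### SAP 5.4 starts the 30 treatment-free days for Clinical Remission at Clinical Response, which normally falls on caplacizumab; read literally, this nearly closes route (a) and derived relapse

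*SAP*

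**What the plan says.** Protocol 9.2.2 gives the definition, "Clinical remission is defined as sustained Clinical Response with no TPE and no anti-vWF therapy", for at least 30 days, with no start date for those days. SAP 3.2.1 repeats it and refers to SAP 5.4 for the derivation. SAP 5.4 supplies the start: "from the date that Clinical Response is achieved".

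Three other rules bear on it:

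- **Assessment period.** SAP 3.2.1 says "Remission is assessed starting from the clinical response (for participants not requiring TPE) or the end of TPE" (the latter for participants who needed TPE), and runs to the end of study.
- **Exacerbation.** SAP 5.4 counts its 30 days from stopping TPE or anti-vWF therapy, not from response.
- **Relapse.** SAP 5.4 requires a prior Clinical Remission and a confirmed ADAMTS13 activity below 10%.

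On timing, Protocol 2.3.2 says of the published TPE-free cases: "All had platelet count recovery within 5 days". Protocol 4.1 says "Caplacizumab treatment will be continued until sustained ADAMTS13 activity level of" at least 50% is seen at two consecutive visits after platelet normalization, or until 12 weeks. It also says "ADAMTS13 activity levels will be obtained once a week starting on Day 8 of caplacizumab treatment".

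**The concern.** Exacerbation, Clinical Remission and relapse are meant to follow one another, but exacerbation is timed from stopping treatment and Clinical Remission from response. Because dosing continues well past platelet recovery, the date that starts the treatment-free count is normally a date on treatment. A programmer who follows SAP 5.4 as written would find almost nobody in Clinical Remission.

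Two results depend on it. Remission (primary and secondary) would rest almost wholly on route (b), ADAMTS13 recovery. Clinical Relapse, which needs Clinical Remission first, would be almost uncountable, even for participants who are responders by route (b). Relapse bears directly on whether a TPE-free regimen gives a durable result.

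**Working it through.** **1. The plan's own figure.** Protocol 9.4 and SAP 4 give a lower 95% Wilson bound of 58% for a 70% responder rate with n = 55. The rate comes from 0.85 × (1 − 0.18) = 0.697. Since 0.70 × 55 = 38.5, rounding up gives 39/55 = 70.9%. The Wilson limits are

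[p + z²/2n ± z√(p(1−p)/n + z²/4n²)] / (1 + z²/n).

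With p = 0.7091, z = 1.96 and n = 55 this is (0.7440 ± 0.1250)/1.0698, or 57.9% to 81.2%. The 58% is reproduced.

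**2. Day count under the literal reading.** Assume Clinical Response on Day 5. The documents give platelet recovery within 5 days but no timing for the LDH criterion. The 30 days are then Days 5 to 34. Two weekly ADAMTS13 values from Day 8 put the earliest rule-based stop nominally at Day 15, or Day 12 with the −3 day visit window. A 12-week course ends on Day 84.

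| Last dose | Dosed days within Days 5–34 | Route (a) met through that response? |
|---|---|---|
| Day 12 | 8 | No |
| Day 15 | 11 | No |
| Day 84 | 30 | No |

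Moving response to Day 4 or Day 8, with last dose on Day 12, 15, 29, 57 or 84, leaves 4 to 80 days of dosing after response, and route (a) fails each time. If any 30 treatment-free days after response count, it is met each time, given the full 84 days of follow-up.

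**3. Who is affected on Remission.** A participant who stops under the ADAMTS13 rule and is in Clinical Response already meets route (b). Those at risk are mainly 12-week completers without ADAMTS13 recovery and early stoppers. Protocol 4.1 expects some such participants: it adds visits "for participants who do not have ADAMTS13 activity levels of" at least 50% at stopping. It does not say how many.

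**4. Illustration for the primary endpoint.** Let k of the 39 planned responders qualify by route (a) only (k is assumed).

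| k | Responders | Rate | 95% Wilson CI |
|---|---|---|---|
| 0 | 39/55 | 70.9% | 57.9–81.2% |
| 1 | 38/55 | 69.1% | 56.0–79.7% |
| 2 | 37/55 | 67.3% | 54.1–78.2% |
| 3 | 36/55 | 65.5% | 52.3–76.6% |

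**5. Relapse.** Without Clinical Remission there can be no derived relapse, and exacerbation closes 30 days after stopping. Days 31 to 84 after stopping, 54 of 84 (64%), are then unclassified. No scheduled visit falls on days 30 to 80 (28 ± 1 gives 27–29; 84 ± 3 gives 81–87), so apart from unscheduled samples the loss occurs at the 12-week visit. For scale, the French triplet cohort in Protocol 2.3.2 had one relapse in 90 (1.1%), and 55 × 1/90 = 0.6 events. That cohort also received TPE, and the figure is not limited to days 31–84. One such relapse, 1/55 = 1.8% (0.3–9.6%), would be reported as 0/55 (0–6.5%). Wilson is assumed here, because the SAP names no interval method for secondary endpoints.

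**6. TPE recipients.** SAP 3.2.1 starts at the end of TPE and SAP 5.4 at Clinical Response. Protocol 4.1 continues TPE for at least 2 days after platelet normalization, so the two dates can differ. This touches secondary Remission only, since TPE recipients cannot be primary responders.

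**7. Follow-up after permanent discontinuation.** Protocol 7.1.1 first keeps these participants to the early discontinuation visit and the 28-day visit (in the Section 1.3.3 schedule, "FU visit 28 days after last dosing", ± 1 day). Its later paragraphs on handling after discontinuation follow them to scheduled study completion. With 27 to 29 days, a 30-day interval cannot be seen under any reading.

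**The case against.** The best defence is that SAP 5.4 only restates the assessment period in SAP 3.2.1: from response onwards, look for any 30 treatment-free days. The appendix does not say first response, although its time-to-event rules specify the initial day or first time where that is meant. A later response date, re-established at off-drug visits, could therefore also serve; that would put Clinical Remission at day 37 to 58 after the last dose. The exacerbation rule itself implies that Clinical Remission follows stopping. A literal reading nearly empties an endpoint route that both documents define, so it is unlikely to be intended.

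This is a fair account of probable intent. It does not settle the derivation, because SAP 3.2.1 sets when assessment begins and SAP 5.4 attaches its date to the 30 days themselves. No other sentence overrides it.

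Other limits also stand. Route (b) protects most of the primary endpoint. A participant who first responds after stopping can still qualify by route (a). A late platelet fall without ADAMTS13 below 10% is not a relapse under any reading. Protocol 8.1.2 also has investigators record relapse as a clinically significant TTP event, so a true relapse would remain in the data even if the derived count missed it.

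**Conclusion.** Wrong as written: the only stated start for the 30 treatment-free days normally falls on treatment. Programmed literally, it biases Remission downward by an unknown and probably small amount (1/55 = 1.8 points per participant who depends on route (a)) and biases derived relapse towards zero. Both effects rest on the literal reading and on response being reached on drug, which the protocol's platelet data and dosing rule make the expected course.

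A reader might infer that the wrong rule has been programmed or that the primary result is materially distorted. The documents support neither: SAP 3.2.1 leans the other way, and the number relying on route (a) is not given. A reader might also note that at k = 3 the lower bound (52.3%) falls below the 54% in the sample-size footnote and call that a failed study. SAP 3.1 sets no success criterion, and k is an assumption. Confidence is medium.

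**What to change.** In SAP 5.4, replace the parenthesis after the 30 days with: *counted from the latest of the date of Clinical Response, the last caplacizumab dose and the last TPE, with Clinical Response sustained (platelets, LDH and no new or progressive ischemic organ injury at available assessments) over those days; after re-treatment for a recurrence, the dates are those of the re-treatment.*

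Keeping response among the three dates prevents days before response from counting. Requiring all three components prevents an LDH rise or new organ injury from being ignored.

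Align SAP 3.2.1 with this wording. Leave the exacerbation rule and the missing-data rules in SAP 5.4 as they are. The two statements in Protocol 7.1.1 on follow-up after permanent discontinuation must also be reconciled.

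The SAP change costs wording and programming only: dosing dates, TPE records and laboratory data are already collected. A participant who first responds after stopping reaches Clinical Remission later than if counted from stopping. For example, response on day 25 after the last dose gives day 25 + 30 = 55 instead of day 30, still inside the 84-day follow-up.
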